**Table 3. Signs and Symptoms for Presenting Indications**

Presenting Indication	Signs and Symptoms	
HABP/VABP/VP mechanically ventilated patients	
 
• Rales;
 
• Dullness on percussion;
 
• Bronchial breath sounds;
 
• Egophony;
 
• Purulent secretion; and
 
	
 
• Fever [1] (oral or tympanic temperature <math>\geq 38^{\circ}\text{C}</math> [<math>\geq 100.4^{\circ}\text{F}</math>] or rectal/core temperature <math>\geq 38.3^{\circ}\text{C}</math> [<math>\geq 100.9^{\circ}\text{F}</math>]) OR hypothermia (rectal/core temperature <math>< 35^{\circ}\text{C}</math> [<math>< 95^{\circ}\text{F}</math>]).
 

HABP/VABP/VP non-mechanically ventilated patients	
 
• Cough;
 
• Rales;
 
• Dullness on percussion;
 
• Bronchial breath sounds;
 
• Egophony;
 
• Dyspnea;
 
	
 
• Respiratory rate <math>> 25</math> breaths/minute; and
 
• Fever [1] (oral or tympanic temperature <math>\geq 38^{\circ}\text{C}</math> [<math>\geq 100.4^{\circ}\text{F}</math>] or rectal/core temperature <math>\geq 38.3^{\circ}\text{C}</math> [<math>\geq 100.9^{\circ}\text{F}</math>]) OR hypothermia (rectal/core temperature <math>< 35^{\circ}\text{C}</math> [<math>< 95^{\circ}\text{F}</math>]).
 

Bacteremia	
 
• Heart rate <math>> 100</math> bpm;
 
• Respiratory rate <math>> 25</math> breaths/minute;
 
• Systolic blood pressure <math>< 90</math> mmHg; and
 
	
 
• Fever [1] (oral or tympanic temperature <math>\geq 38^{\circ}\text{C}</math> [<math>\geq 100.4^{\circ}\text{F}</math>] or rectal/core temperature <math>\geq 38.3^{\circ}\text{C}</math> [<math>\geq 100.9^{\circ}\text{F}</math>]) OR hypothermia (rectal/core temperature <math>< 35^{\circ}\text{C}</math> [<math>< 95^{\circ}\text{F}</math>]).
 

cUTI or AP	
 
• Urinary frequency;
 
• Urinary urgency;
 
• Dysuria;
 
• Nausea;
 
• Vomiting;
 
• Abdominal pain;
 
• Supra-pubic pain or discomfort;
 
	
 
• Flank pain;
 
• Costovertebral angle tenderness on examination; and
 
• Fever [1] (oral or tympanic temperature <math>\geq 38^{\circ}\text{C}</math> [<math>\geq 100.4^{\circ}\text{F}</math>] or rectal/core temperature <math>\geq 38.3^{\circ}\text{C}</math> [<math>\geq 100.9^{\circ}\text{F}</math>]) OR hypothermia (rectal/core temperature <math>< 35^{\circ}\text{C}</math> [<math>< 95^{\circ}\text{F}</math>]).
 

Surgical and post-traumatic wound infections	
 
• Purulent drainage;
 
• Erythema;
 
• Warmth;
 
• Exudation;
 
• Odor;
 
• Pain;
 
	
 
• Leukocytosis; and
 
• Fever [1] (oral or tympanic temperature <math>\geq 38^{\circ}\text{C}</math> [<math>\geq 100.4^{\circ}\text{F}</math>] or rectal/core temperature <math>\geq 38.3^{\circ}\text{C}</math> [<math>\geq 100.9^{\circ}\text{F}</math>]) OR hypothermia (rectal/core temperature <math>< 35^{\circ}\text{C}</math> [<math>< 95^{\circ}\text{F}</math>]).
 

1. Maximum daily temperature on a single treatment day will be recorded. Note: Axial temperature is not allowed.            AP = acute pyelonephritis; bpm = beats per minute; cUTI = complicated urinary tract infection; HABP = hospital-acquired bacterial pneumonia; VABP = ventilator-associated bacterial pneumonia; VP = ventilated pneumonia.
		

## 7.6 Clinical Outcome

Clinical outcome will be used to determine a response of clinical success for all patients. Based on the assessment of signs and symptoms, the unblinded Investigator will choose 1 of the following clinical outcomes at the Day 5, Day 7, EOT Visit, TOC Visit, LFU Visit, and ET Visit, if applicable. In Part A, in addition to the unblinded Investigator, a blinded assessor will also determine clinical outcome. If there is a discrepancy between the assessment of the blinded assessor and unblinded Investigator, the assessment from the blinded assessor will be used. If there is a missing assessment from either the blinded assessor or unblinded Investigator, the other available assessment will be used (see [Section 5.4.1](#)). An adjudication committee may be organized for endpoint adjudication should it be deemed necessary by the DSMB. In such a case, a charter will be developed that describes their activities.

Clinical cure: complete resolution or significant improvement of signs and symptoms that were present at baseline and no new symptoms, such that no additional Gram negative antimicrobial therapy is warranted.

Clinical failure: symptoms present at study entry have not significantly improved or completely resolved, or new symptoms have developed and require the initiation of a non-study Gram negative antibacterial drug therapy, death, or intolerance to study drug leading to discontinuation from the study treatment.

Clinical indeterminate: determination cannot be made because of missing data or the patient is lost to follow-up.

## 7.7 Microbiologic Assessments

To assess the primary indication and follow-up of the primary indication, all specimens will be sent to the local laboratory for culture and susceptibility testing per institutional standards. Pure cultures of isolated pathogens will be shipped from the local laboratory to the central laboratory for confirmation of species identification, susceptibility testing, and possible molecular characterization, as detailed in the Microbiology Laboratory Manual. Definitions of resistance for purposes of this protocol are detailed in [Section 9.1](#) and in the Microbiology Laboratory Manual.

Rapid diagnosis of ABC HABP/VABP/VP will utilize the BPP to detect ABC in respiratory specimens. Details of the test and its use will be included in the Laboratory Manual. The test results will be recorded in the eCRF.

All patients must have a specimen sample from the site of infection (ie, respiratory secretion, blood, urine, or wound) and 2 sets of blood culture samples from 2 separate venipuncture sites collected at Screening. Screening respiratory specimens for patients with suspected HABP/VABP/VP should be subjected to BPP rapid diagnostic testing as detailed above, where available, and submitted to the local microbiology laboratory for culture and susceptibility testing. In these cases, if the local microbiology laboratory culture does not grow ABC, the patient will be withdrawn from the study drug treatment.

If the screening sample for culture that is growing ABC is taken per standard of care before the patient or patient's legally authorized representative signs informed consent, that isolate may be used for baseline eligibility and sent to the central laboratory once consent is obtained, as long as the sample was collected within 72 hours prior to randomization. Additional samples for baseline culture should be collected again within 24 hours prior to randomization, at the time points specified in the Schedule of Procedures ([Appendix A](#)), and if clinically indicated. Patients who are failing their current treatment as evidenced by worsening clinical condition may enroll in the study, provided they meet all other requisites. However, additional samples must be taken from the site of infection within 24 hours prior to randomization and sent to the local laboratory for culture.

The local laboratory will culture each sample for species identification, quantification (urine and BAL only), and susceptibility testing. Any organism isolated from the culture will be identified by genus and species by the local laboratory. Potential pathogen(s) cultured at the local laboratory, including species isolated from mixed infections with other Gram positive or Gram negative organisms, will be sent to a designated central laboratory for confirmation of species identification, susceptibility testing results, and potential molecular characterization.

All organisms identified on culture at the local laboratory and the local laboratory assessment of susceptibility testing for each organism will be captured in the eCRF.

Enrollment in Part A can occur after ABC is identified in the blood and/or other respiratory tract specimens but prior to establishing the resistance profile. If local laboratory susceptibility testing reveals colistin resistance after a patient has been randomized to Part A, the patient must be transferred to Part B, regardless of the treatment group assignment in Part A, once Part B is open for enrollment. If Part B is not open for enrollment, patients will be withdrawn from the study drug treatment.

Patients who are randomized to Part A based on a positive screening of a respiratory sample for ABC by BPP rapid test, but subsequently do not have growth of ABC in their respiratory sample culture processed by the local microbiology laboratory, will be withdrawn from the study drug treatment. The need for continued standard of care treatment should be assessed by the Investigator.

When a patient's culture grows Gram positive organisms but the patient is clinically improving, the patient may remain on study drug without additional Gram positive antibiotic coverage at the Investigator's discretion. Patients who are not clinically improving or need adjustment in antimicrobial therapy that is not allowed per the protocol should be discontinued from study drug at the discretion of the Investigator, but should remain in the study to complete all study assessments. Additional cultures and all EOT procedures should be performed at the time of discontinuation and every attempt must be made to collect survival data at Day 28 or anytime thereafter.

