### 3 STUDY DESCRIPTION

#### 3.1 Summary of Study Design

This study is a randomized, active-controlled study to evaluate the safety and efficacy of IV ETX2514SUL in patients with ABC infections. Patients providing informed consent and meeting all study eligibility criteria will be enrolled in the study and have pretreatment blood and infection site-specific samples obtained and submitted to the local laboratory.

The study will be enrolled in 2 parallel parts, with the PK data from the first approximately 30 patients in Part A (with only 15 patients dosed with ETX2514SUL) reviewed prior to initiating enrollment in Part B:

- a. Part A will be the pivotal, assessor-blind, randomized, comparative portion of the study in patients with documented ABC HABP, VABP, VP, or bacteremia. While study drugs will not be masked due to logistical reasons, every attempt will be made to maintain the blind for patients, all staff at the site, and the Sponsor or its designees, except for the treatment physician and other immediate healthcare providers (see [Section 5.4](#)). In Part A, patients will be randomized 1:1 to 1 of the following treatment groups:
  - Group 1: 1.0 g ETX2514/1.0 g sulbactam IV infused over 3 hours q6h plus 1.0 g imipenem/1.0 g cilastatin IV infused over 1 hour q6h; or
  - Group 2: 2.5 mg/kg colistin IV infused over 30 minutes every 12 hours (q12h) plus 1.0 g imipenem/1.0 g cilastatin IV infused over 1 hour q6h.

Patients will be enrolled until there are 120 patients in the CRABC Microbiologically Modified Intent-to-Treat (m-MITT) Population in Part A, as determined by the central microbiology laboratory. Approximately 200 patients are expected to be enrolled in Part A, assuming approximately 60% of patients will have CRABC (see [Section 9](#) for complete details). The HABP/VABP/VP patients who are randomized to Part A based on a positive screening of a respiratory sample for ABC by the Biofire® FilmArray® 2.0 Pneumonia Panel (BPP), but who subsequently do not have growth of ABC in their respiratory sample culture processed by the local microbiology laboratory, will be withdrawn from the study drug treatment.

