Transfer from Part A to Part B: Since Part A will be the first time patients in intensive care are receiving ETX2514SUL, PK in the first approximately 30 patients must be verified prior to initiating Part B to ensure the treatment planned in Part B is optimal for the targeted patient population. Patients randomized to either group of Part A can only be transferred to Part B, once Part B is open for enrollment, if the ABC identified from the baseline culture is subsequently determined to be resistant to colistin or polymyxin B by the local microbiology laboratory. If Part B is not yet open for enrollment in a given country and a patient in Part A has a baseline culture determined to be colistin- or polymyxin B-resistant but is responding to therapy, the patient may remain in Part A at the discretion of the Investigator. A patient in Part A whose culture is determined to be colistin- or polymyxin B-resistant and who has not shown improvement or whose condition has worsened will be withdrawn from the study drug treatment. All such cases must be discussed with the Medical Monitor.

Any organism isolated from the blood or infection site-specific cultures will be identified by genus and species by the local laboratory. Organisms will be cultured and quantified (urine and bronchoalveolar lavage [BAL] only) at the local laboratory, and susceptibility of the organism(s) will be performed per local laboratory standards. Isolates of pathogens cultured at the local laboratory are to be sent to the central laboratory for confirmation of identification and susceptibility testing.

[figure not shown]

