23. Participation in a clinical study involving investigational medication or an investigational device within the last 30 days or 5 half-lives, whichever is longer, prior to Day 1;
24. Any condition that, in the opinion of the Investigator, would compromise the safety of the patient or the quality of the data or require greater than 14 days of treatment with antibiotics;
25. Unable or unwilling, in the opinion of the Investigator, to comply with the protocol;
26. Has previously received ETX2514 in this study; or
27. For Part A only, patients with an infection known to be resistant to colistin or polymyxin B (defined as MIC  $\geq$ 4 mg/L by a non-agar based method), with a known intolerance to colistin, or taking any drug that prevents them from receiving colistin.

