### 9.2.2 Analysis of Efficacy

#### 9.2.2.1 Primary efficacy analysis

The primary efficacy endpoint for the study is 28-day all-cause mortality in the CRABC m-MITT Population in Part A. Patients in the CRABC m-MITT Population who discontinue study drug prematurely in Part A for any reason will be included in the assessment of 28-day all-cause mortality, provided consent has not been withdrawn.

A sensitivity analysis for the primary efficacy endpoint will be performed for patients whose eligible culture is >48 hours from the first dose of study drug, as well as for all patients with and without evidence of non-susceptibility to colistin and ETX2514SUL at baseline. Details of the sensitivity analysis will be described in the SAP.

The non-inferiority assessment will be based on the 2-sided 95% confidence intervals (CIs) for the difference ( $[\text{ETX2514SUL} + \text{imipenem/cilastatin}] - [\text{colistin} + \text{imipenem/cilastatin}]$ ) in 28-day all-cause mortality rates between the treatment groups. Non-inferiority will be concluded if the upper limit of the 2-sided 95% CI is less than +20%.

If non-inferiority is achieved, a test of superiority will be performed.

The analysis of the primary efficacy endpoint 28-day all-cause mortality will also be performed in the ITT Population.

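### While Part B is closed, Protocol 7.7 and Protocol 3.1 disagree on study drug for responding Part A patients with local colistin resistance; separately, no analysis in the primary population restores transferred patients who are centrally susceptible (minor)

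*Protocol*

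**What the plan says.** **Study drug while Part B is closed.** Protocol 3.1 addresses a country where Part B has not opened and a Part A patient whose baseline isolate proves resistant to colistin or polymyxin B. If that patient is responding, "the patient may remain in Part A at the discretion of the Investigator". A patient "who has not shown improvement or whose condition has worsened will be withdrawn from the study drug treatment". All such cases go to the Medical Monitor. The synopsis and SAP 3.1 repeat this. Protocol 7.7 covers the same situation for colistin resistance and makes no exception for responders: "If Part B is not open for enrollment, patients will be withdrawn from the study drug treatment".

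**Once Part B is open.** Protocol 7.7 says that "the patient must be transferred to Part B, regardless of the treatment group assignment in Part A, once Part B is open for enrollment". Protocol 3.1 permits transfer only on a local finding of colistin or polymyxin B resistance.

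**When Part B opens.** Protocol 3.1 requires review before Part B starts, "with the PK data from the first approximately 30 patients in Part A", and recognizes that opening can differ by country.

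**Analysis.** Under Protocol 9.1 and SAP 8.4, transfer from Part A to Part B is an exclusion from the Part A CRABC m-MITT Population in its own right. The exclusion for resistance to colistin or ETX2514SUL is separate and rests on the central laboratory. SAP 9.3, 9.3.1 and 9.3.2 keep transferred patients out of Part A efficacy. One sensitivity analysis in SAP 9.3.1 includes them, in the ITT Population. Patients who only stop drug are kept: Protocol 9.2.2.1 says that those "who discontinue study drug prematurely in Part A for any reason will be included in the assessment of 28-day all-cause mortality", unless consent is withdrawn.

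**The concern.** There are two separate issues.

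First, a site that keeps a responder on drug while Part B is closed follows 3.1 and breaches 7.7; a site that stops drug follows 7.7 and does not use the discretion in 3.1. The Medical Monitor must be consulted, but no text says which section governs. At stake is whether a severely ill patient who is improving loses study drug.

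Second, transfer follows the local result, while the resistance exclusion follows the central one. The two can differ: at local sites "susceptibility of the organism(s) will be performed per local laboratory standards", whereas the Part A exclusion criterion defines colistin resistance as an MIC of at least 4 mg/L "by a non-agar based method), with a known intolerance to colistin". A locally resistant, centrally susceptible patient with CRABC who dies before transfer is counted in the primary analysis; one who is transferred is not. That is an exclusion by a post-randomization event, and no planned analysis in the primary population examines it.

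**Working it through.** **1. Who is in conflict while Part B is closed**

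| Patient with local colistin resistance | Protocol 3.1, synopsis, SAP 3.1 | Protocol 7.7 |
|---|---|---|
| Responding | May remain, Investigator's discretion | Withdrawn from study drug |
| Not improved or worse | Withdrawn from study drug | Withdrawn from study drug |

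Only the first row conflicts. At least about the first 30 of about 200 Part A patients enter before Part B opens: 30/200 = 15%. The documents give no local resistance rate. Assuming 2% to 10%, 0.02 × 30 = 0.6 to 0.10 × 30 = 3 of these are locally resistant. Those in conflict are the responders among them, a fraction the documents do not give, plus responders in countries where Part B opens later.

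**2. The planned sample size**

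Inputs (Protocol 9.2.5): mortality 41% control and 36% test, margin 20%, 2-sided 95% CI, 80% power.

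n per arm = (1.96 + 0.84)² × (0.41×0.59 + 0.36×0.64) / (0.20 + 0.05)² = 7.849 × 0.4723 / 0.0625 = 59.3, so 60 per arm and 120 in total. This reproduces the plan. Power at 60 per arm is 80.5%, or 74.9% with the continuity correction of SAP 9.3.1.

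Enrollment runs until 120 patients are in CRABC m-MITT. Transfers lie outside that count, so they cost no planned power, and their effect is properly shown by adding them to 60 per arm.

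**3. Adding transfers back**

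Upper limit (ETX2514SUL minus colistin) = p1 − p2 + 1.96 × √[p1(1−p1)/n1 + p2(1−p2)/n2] + ½(1/n1 + 1/n2). This is my reading of the continuity-corrected interval in SAP 9.3.1.

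Base near the design rates, 22/60 v 25/60: −5.00 + 1.96 × 8.90 + 1.67 = 14.1%. The most adverse case adds k ETX2514SUL deaths and k colistin survivors:

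| k per arm | Deaths | Upper limit |
|---|---|---|
| 1 | 23/61 v 25/61 | 15.7% |
| 2 | 24/62 v 25/62 | 17.2% |
| 3 | 25/63 v 25/63 | 18.7% |
| 4 | 26/64 v 25/64 | 20.1% |

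The most favorable case at k = 3, 22/63 v 28/63, gives 9.1%. Three per arm with the same outcome barely matter: all deaths, 25/63 v 28/63, 14.1%; all survivors, 22/63 v 25/63, 13.7%.

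Borderline base, 25/60 v 25/60: 0 + 1.96 × 9.00 + 1.67 = 19.3%. One added ETX2514SUL death, 26/61 v 25/60, gives 0.96 + 1.96 × 8.98 + 1.65 = 20.2%. One added ETX2514SUL survivor, 25/61 v 25/60, gives 18.5%.

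**4. Whether a planned analysis already covers this**

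The susceptibility and culture-timing sensitivity analyses run inside CRABC m-MITT, after transfers have gone. SAP 8.7 nests CRABC ME in CRABC m-MITT. The repeat analyses restore only patients who withdrew consent. Part B has its own CRABC m-MITT definition, but Part B is single-group and descriptive. That leaves the ITT analysis, which also holds carbapenem-susceptible and culture-negative patients.

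**The case against.** The case for leaving the plan alone has five parts.

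- **Site variation comes mostly from discretion.** Protocol 3.1 alone lets one Investigator keep a responder and another not, and a harmonized rule that retains discretion keeps that. This stands: the fix removes the contradiction and only part of the variation.
- **The window may have passed.** SAP 7.1 describes the intense PK sampling of about 30 patients in the past tense. If that cohort is complete, the wording now matters mainly in countries where Part B opens late. This stands as a limit on reach.
- **Few discordant transfers are likely.** At 2% local resistance, 200 × 0.02 = 4 patients; if 60% are carbapenem-resistant, 2.4 are CRABC, so one discordant transfer per arm needs 2/2.4 = 83% discordance. At 10%, 200 × 0.10 × 0.60 = 12, and three per arm needs 6/12 = 50%. The Microbiology Laboratory Manual, not available here, may narrow discordance further. This makes the larger rows of the table unlikely but does not exclude a single case.
- **ITT already restores transfers.** That is a standard check and keeps every randomized patient, but it does not isolate the effect in the population that carries the non-inferiority claim.
- **The added analysis is diluted.** Colistin-arm transfers go on to receive ETX2514SUL, which can pull the arms together and favor non-inferiority. This stands, and is why it should be a sensitivity analysis only.

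A reader might also infer that the two sections contradict each other once Part B is open. They do not: a rule that transfer is allowed only on local resistance and a rule that it is then mandatory can both be obeyed. The wording is loose, since the withdrawal sentence in 3.1 is not expressly limited to Part B being closed, and 7.7 names colistin alone where 3.1 adds polymyxin B.

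**Conclusion.** Both points hold, and both are minor.

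The contradiction is real for responders while Part B is closed. A reader might infer that it distorts the primary analysis. The documents do not support that: stopping drug does not remove a patient from the Day 28 assessment, and a centrally confirmed colistin-resistant isolate is excluded from CRABC m-MITT in any case. Nor does it reach every locally resistant patient, since both sections withdraw those who are not improving.

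The transfer exclusion is a genuine post-randomization exclusion without a check in the primary population. A reader might infer that it threatens the non-inferiority conclusion or the planned power. It does not affect planned power, because enrollment continues to 120. Near the design rates, it takes four added patients per arm, all with the most adverse outcomes, to pass 20%. A result already close to the margin could move on one patient. The documents give neither the number of transfers nor the local-central discordance, so these are illustrations under assumed counts, and the direction of any bias is unknown.

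**What to change.** 1. **Amend Protocol 7.7 to match 3.1**, and use the same clarified wording in the synopsis, Protocol 3.1 and SAP 3.1. Part B open: transfer is mandatory in both arms on local baseline resistance to colistin or polymyxin B. Part B closed: a responder may remain after Medical Monitor discussion; a non-responder is withdrawn from study drug. All are followed to Day 28.
2. **Keep the primary population and add one sensitivity analysis to SAP 9.3.1.** It should add transferred patients who meet all other CRABC m-MITT criteria, including no central resistance to colistin or ETX2514SUL, by randomized arm with Day 28 status. State that colistin-arm transfers then receive ETX2514SUL, which can pull the arms together.

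Optionally, show paired local and central colistin results for transferred patients in the exclusion listing already planned in SAP 9.2.1, so that the number affected becomes visible.

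The cost is clarifying text and one extra analysis. Local susceptibility is already captured in the eCRF, isolates already go to the central laboratory, and Day 28 survival is already sought for all randomized patients who have not withdrawn consent.
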